8.1. Efficacy Assessments

The sequence of all trial related procedures including the relationship of procedures relative to dosing should be followed as detailed in the Study Manual.

8.1.1. ALSFRS-R

The ALSFRS-R will be performed at each study visit (both in-clinic and remote) as described in the Study Manual. MiToS staging will be determined based upon the responses on the applicable items of the ALSFRS-R.

8.1.2. Pulmonary Function Assessment

The pulmonary function assessment in this trial will be FVC. Pulmonary function assessment will be performed in the clinic at all in-clinic study visits (Screening, Day 1, Week 4, Week 12, Week 24, Week 36, Week 48 and Follow-up [FU]), safety permitting, as described in the Study Manual. It will also be performed using the home spirometer ± 2 days of the date of the in-clinic visits for Weeks 4, 12, and 36 in addition to 1 to 3 days prior to Day 1, Weeks 24, 48 and FU as shown in [Table 3](#). Finally, it will be done using the home spirometer during the scheduled remote visits at Weeks 8, 16, 20, 28, 32, 40, and 44. If a patient can be seen in the clinic for screening, but FVC cannot be performed for safety reasons, the patient will be provided a home spirometer and perform a home FVC within 2 days following the screening visit; that value will be used for eligibility. If on subsequent in-clinic visits, the FVC cannot be performed in the clinic for safety reasons, that should be documented and only the home FVC linked to that in-clinic visit will be obtained. For all home FVC testing, the test will be performed during a telemedicine call with a trained FVC evaluator.

When an FVC falls below 50%, the site will record if the potential use of NIV was discussed, and if the patient refuses NIV, the reason(s) for the refusal. Details can be found in the Study Manual.

8.1.3. Hand Grip Strength

Hand grip strength will be assessed at all in-clinic study visits as described in the Study Manual. If an in-clinic visit needs to become a remote visit, it will not be performed.

8.1.4. Muscle Strength

Muscle strength measurements of selected muscles will be performed using HHD at all in-clinic study visits as described in the Study Manual. If an in-clinic visit needs to become a remote visit, it will not be performed.

8.1.5. Health Economic Outcomes Measures

During the course of the trial, if the patient is prescribed and agrees to obtain, and/or receives any of the following durable medical equipment (DME), reason for obtaining, timing and extent of use will be recorded as described in the Study Manual:

- Non-invasive ventilation (including type of device)
- Gastrostomy tube
- Manual wheelchair
- Power wheelchair
- Augmentative and alternative communication (including type of device)

Obtaining information about the DME use should be obtained at every in-clinic and remote visit.

EQ-5D-5L and the EQ-VAS are standardized measures of health status developed by the EuroQol Group in order to provide a simple, generic measure of health for clinical and economic appraisal. They will be administered at time points as indicated in the SoA ([Section 1.3](#)) and as described in the Study Manual. If an in-clinic visit in which the EQ-5D-5L and the EQ-VAS are scheduled to be performed becomes a remote visit, they will both still be obtained.

8.1.6. Quality of Life

The following quality of life questionnaire will be utilized at multiple study visits as specified in the SoA ([Section 1.3](#)) and described in the Study Manual:

- ALSAQ-40

If an in-clinic visit in which the ALSAQ-40 is scheduled to be performed becomes a remote visit, the ALSAQ-40 will still be obtained.

8.1.7. Structured Patient Interviews

At a subset of participating US centers, English language-speaking patients enrolled will have a qualitative patient interview within two weeks of completing the Week 24 visit (sometime between Week 22 and Week 24).

The interview will be conducted by phone and will collect information in the patient's words regarding their perceptions of functionality and ALS symptom burden, activities of daily living, and experiences in the trial.

8.1.8. Hospitalizations

Hospitalizations experienced by a patient following randomization and occurring in the context of a serious adverse event will be determined by the Investigator as being either related to ALS, unrelated to ALS, or indeterminate. Hospitalizations deemed related to ALS cover those that are

both related to disease progression, hospitalizations that may occur to address an ongoing ALS symptom or to be preventative (such as hospitalization for a PEG / RIG tube), as well as those to address a complication of a treatment being received for ALS. This information will be recorded and entered into the EDC. Hospitalizations that are for social reasons, or those that were planned prior to the patient signing the ICF are not considered SAEs and therefore relationship to ALS will not be recorded. Further details are described in the Study Manual.

8.2. Safety Assessments

Planned time points for all safety assessments are provided in the SoA ([Section 1.3](#)).

8.2.1. Physical Examinations

A routine physical examination will be performed at Screening, and an abbreviated physical examination (consisting of an examination of general appearance, skin, lungs, cardiovascular and abdomen) will be performed at the Follow-Up visit. If the Follow-up visit is converted to a remote visit, the parts of the exam that can be done utilizing telemedicine/video call should be performed.

8.2.2. Vital Signs

Heart rate, blood pressure, and respiratory rate (measured after the patient has been resting and seated for at least 3 minutes), will be obtained at all in-clinic study visits. Temperature will also be obtained at the Screening visit. Height is obtained only at the screening visit; it should only be a historical height if the patient is unable to stand. Weight will be obtained at each in-clinic study visit; and body mass index (BMI) will be calculated at screening and subsequent visits. If the pulse is <50 or >100 bpm, mean systolic blood pressure <90 or >160 mm Hg; mean diastolic blood pressure <50 or >100 mm Hg or the respiratory rate is <10 or >20 breaths per minute, the out of range vital sign should be re-checked following the patient resting for 10 minutes in the seated position. If the in-clinic visit is converted to a remote visit, vital signs will not be performed.

8.2.3. Electrocardiograms

A 12-lead ECG will be obtained as outlined in the SoA ([Section 1.3](#)) using an ECG machine that automatically calculates the heart rate and measures PR, QRS, QT, and QTc intervals.

Patients should be sitting or supine prior to the ECG for at least 5 minutes. The investigator may perform additional ECG recordings as needed for the care of the patient.

For safety monitoring purposes, the investigator or designee must review, sign, and date all ECG tracings.

Unscheduled ECGs may be collected at additional time points, for example in case of an AE or based on vital signs, as determined by the investigator or the Medical Monitor.

All ECG tracings will be kept as part of the patient's permanent study file at the clinical site. Digital recordings will be analyzed and stored at a central ECG laboratory.

If an in-clinic visit is converted to a remote visit, an ECG will not be obtained.

8.2.4. Neurological Examinations

A brief neurological exam will include assessments of specific cranial nerves (eye, face, and tongue movements), motor strength in specific muscles, evaluation of deep tendon and bilateral plantar reflexes, sensory testing, and tests of co-ordination (limited to finger-to-nose and heel-to-shin when possible to assess). This will be administered at screening, Week 24, and at Follow-Up visit as described in the Study Manual. If the Week 24 or Follow-up visits are converted to a remote visit, the parts of the exam that can be performed using telemedicine/video call should be performed.

8.2.5. Laboratory Assessments

See Appendix 2 ([Section 10.2](#)) for the list of clinical laboratory tests to be performed and see the SoA ([Section 1.3](#)) for the timing and frequency.

The investigator must review the laboratory report, document this review, and record any clinically relevant changes occurring during the trial in the AE section of the CRF. Clinically significant abnormal laboratory findings are those which are not associated with the underlying disease; if the abnormal laboratory finding is felt to be associated with the underlying disease but is judged by the investigator to be more severe than expected for the patient's condition it should be recorded as such.

All protocol-required laboratory assessments, as defined in Appendix 2 ([Section 10.2](#)), must be conducted in accordance with the laboratory manual and the SoA ([Section 1.3](#)).

8.2.6. Beck Depression Inventory-Fast Screen (BDI-Fast Screen)

The BDI-Fast Screen will be assessed at all in-clinic study visits as described in the Study Manual. If an in-clinic visit is converted to a remote visit, the BDI-Fast Screen will not be obtained; however, while asking the patient about adverse events, the site will query the patient about symptoms of depression or suicidal thoughts.

8.3. Adverse Events and Serious Adverse Events

8.3.1. Adverse Events

8.3.1.1. Definition of Adverse Event

An AE is defined as any untoward medical occurrence in a patient or clinical investigation patient administered a pharmaceutical product and which does not necessarily have a causal relationship with this treatment. An AE can therefore be any unfavorable and unintended sign (including an abnormal laboratory finding), symptom, or disease temporally associated with the use of study drug, whether or not related to study drug.

Adverse events include:

- Exacerbation of a chronic or intermittent pre-existing condition including either an increase in frequency and/or intensity of the condition.
- New conditions detected or diagnosed after IP administration even though it may have been present before the start of the trial.

- Abnormal assessments, eg, change on physical examination, ECG findings, if they represent a clinically significant finding that was not present at trial start or worsened during the course of the trial.
- Laboratory test abnormalities if they represent a clinically significant finding, symptomatic or not, which was not present at trial start or worsened during the course of the trial, require treatment, or led to dose reduction, interruption or permanent discontinuation of IP. In general, abnormal laboratory findings without clinical significance (based on the investigator's judgment) are not to be recorded as adverse events. Where applicable, clinical sequelae (not the laboratory abnormality) are to be recorded as the adverse event.
- Signs, symptoms, or the clinical sequelae of a suspected drug-drug interaction.
- Signs, symptoms, or the clinical sequelae of a suspected overdose of either study drug or a concomitant medication. Overdose per se will not be reported as an AE/SAE unless it is an intentional overdose taken with possible suicidal/self-harming intent. Such overdoses should be reported regardless of sequelae.

8.3.1.2. Definition of Serious Adverse Event

A **SAE** is defined as any untoward medical occurrence that at any dose:

- Results in death
- Is life threatening, NOTE: The term "life-threatening" in the definition of "serious" refers to an event in which the patient was at risk of death at the time of the event; it does not refer to an event which hypothetically might have caused death if it were more severe
- Requires inpatient hospitalization or prolongation of existing hospitalization
- Results in persistent or significant disability/incapacity, or
- Is a congenital anomaly/birth defect
- Is an important medical event

Medical and scientific judgement should be exercised in deciding whether expedited reporting is appropriate in other situations, such as important medical events that may not be immediately life-threatening or result in death or hospitalization but may jeopardize the patient or may require intervention to prevent one of the other outcomes listed in the definition above. These should also usually be considered serious. Examples of such events include invasive or malignant cancers; intensive treatment in an emergency room or at home for allergic bronchospasm; blood dyscrasias or convulsions that do not result in hospitalization; or development of drug dependency or drug abuse.

An adverse event would meet the criterion of "requires hospitalization," if the event necessitated an admission to a health care facility (eg, overnight stay).

The following reasons for hospitalization are exempted from being reported:

- Hospitalization for cosmetic elective surgery, or social and/or convenience reasons.

- Hospitalization for pre-planned (ie, planned prior to signing informed consent) surgery or standard monitoring of a pre-existing disease or medical condition that did not worsen, eg, hospitalization for coronary angiography in a patient with stable angina pectoris.

However, complications that occur during an exempted hospitalization are AEs or SAEs (for example if a complication prolongs a pre-planned hospitalization).

8.3.1.3. Severity of Adverse Events

The investigator must assess the severity for each AE and SAE reported during the trial.

Severity describes the intensity (severity) of a specific event and is different from seriousness, which is based on patient/event outcome or action criteria and serves as a guide to determine the regulatory reporting obligations. The severity should be assessed by assigning a Grade of 1, 2, 3, 4 or 5 according to the Common Terminology Criteria for Adverse Events (CTCAE), version 5.0, as defined below:

- Grade 1 (Mild): asymptomatic or mild symptoms; clinical or diagnostic observations only; intervention not indicated.
- Grade 2 (Moderate): minimal, local or non-invasive intervention indicated; limiting age-appropriate instrumental ADL*.
- Grade 3 (Severe): Severe or medically significant but not immediately life-threatening; hospitalization or prolongation of hospitalization indicated; disabling; limiting self care ADL**.
- Grade 4 (Life-Threatening): Life-threatening consequences; urgent intervention is indicated
- Grade 5 (Fatal): Death related to AE

* Instrumental ADL refers to preparing meals, shopping for groceries or clothes, using the telephone, managing money, etc.

**Self care ADL refers to bathing, dressing and undressing, feeding self, using the toilet, taking medications, and not bedridden.

If the severity of an AE worsens during IP administration, only the worst severity should be reported on the AE page. If the AE lessens in intensity, no change in the severity is required.

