6. INVESTIGATIONAL PRODUCT

This section describes any study drug: investigational product (IP) (ie, reldesemtiv) or placebo intended to be administered to a trial patient according to the protocol.

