9.4.5.1. Adverse Events

All AE terms will be coded using the Medical Dictionary for Regulatory Activities (MedDRA). Primary system organ class (SOC) and preferred term (PT) of the TEAEs will be tabulated by the early-start and delayed-start treatment groups and periods (placebo-controlled period and active drug period). TEAEs will also be summarized by severity and relationship to study drug. AEs that led to early discontinuation from treatment or the trial and events of special interest will be summarized. Listings will be presented for patients who discontinued due to TEAEs.

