**Duration of treatment:**

The treatment period of the study is 48 weeks. Patients randomized to receive 300 mg reldesemtiv twice a day for a 600 mg TDD will receive reldesemtiv for the entire 48-week treatment period; patients randomized to receive placebo twice daily will receive placebo for the first 24 weeks and receive reldesemtiv for the next 24 weeks.

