### **9.2. Adverse Event Preferred Term and Body/Organ System Summary Tables**

#### **9.2.1. Summaries of Adverse Event Incidence Rates for All Subjects**

All AE terms will be coded using the Medical Dictionary for Regulatory Activities (MedDRA). TEAEs and TESAEs will be summarized by primary SOC and PT, by PT, and also by severity (Grades 1 to 5) and relationship to study drug (related and not related). For a TEAE reported more than once from a patient, the TEAE will be counted only once in the SOC or PT category using the most severe occurrence and/or closer relationship to the study drug. All AEs will be listed.

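### The AE page keeps only the worst grade across the Week 24 switch, so the double-blind placebo severity tables can carry grades reached on reldesemtiv

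*Protocol*

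**What the plan says.** Protocol 8.3.1.3 sets the capture rule: "If the severity of an AE worsens during IP administration, only the worst severity should be reported on the AE page". It adds that a later fall in intensity needs no update. Neither document asks for the grade at the switch or the date of a grade change.

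Protocol section 6 describes study drug as "investigational product (IP) (ie, reldesemtiv) or placebo". Whether IP is read there as reldesemtiv alone or as either product, worsening after Week 24 falls under the rule. The SAP summary (Duration of treatment) says that patients randomized to placebo "will receive placebo for the first 24 weeks and receive reldesemtiv for the next 24 weeks".

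For analysis, Protocol 9.4.5.1 has treatment-emergent AEs (TEAEs) "tabulated by the early-start and delayed-start treatment groups and periods (placebo-controlled period and active drug period"), and adds that "TEAEs will also be summarized by severity and relationship to study drug". SAP 9.2.1 summarizes them "also by severity (Grades 1 to 5) and relationship to study drug". For repeated reports in one patient, "the TEAE will be counted only once in the SOC or PT category using the most severe occurrence". That rule is not limited to occurrences within one period.

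Under Protocol 9.4.1.2 the database is locked after Week 48 and safety follow-up.

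**The concern.** One grade per AE is adequate when a patient stays on one treatment. Here the delayed-start arm receives two treatments in sequence, and the stored grade does not say under which of them it was reached. A by-period severity table needs exactly that information.

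At stake is how severity is attributed in the only randomized, placebo-controlled period, and how visible worsening on first exposure to reldesemtiv is in the active drug period. Protocol 2.3.1 reports that fatigue and nausea appeared to become more frequent with dose in CY 5022. Both are symptoms that could plausibly be present at low grade on placebo and worsen on drug.

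**Working it through.** The plan states no figure on this point, so the check traces the rules and then gives a scale.

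**1. Rules that might separate the periods.**
- SAP 6.7.5 and 12.3 keep data from before and after the transition apart, but for visit measurements, not AE records.
- SAP 9.2.2 imputes both AE onset and AE end dates. These could support assignment by onset or by overlap; the SAP chooses neither.
- Neither document defines a TEAE.
- Protocol 8.3.1.1 counts exacerbation of a pre-existing condition as an AE. It does not say that a placebo-period AE becomes a new AE at the switch, and 8.3.1.3 is the specific rule for an AE that worsens.

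**2. One AE under each possible assignment.** A delayed-start patient has fatigue from Day 150, Grade 1, which becomes Grade 3 on Day 190. Week 24 is scheduled for Day 169 (SAP Table 9). The AE page holds one entry: onset Day 150, Grade 3.

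| Assignment | Double-blind placebo column | Active drug period |
|---|---|---|
| By onset | Grade 3 | not counted |
| Every period spanned | Grade 3 | Grade 3 |
| Split at worsening | Grade 1 | Grade 3 |

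The third row is the correct attribution, but the capture rule does not collect the data for it. The first two rows both put a grade reached on reldesemtiv in the placebo column.

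**3. Both arms.** Inputs: 555 randomized 2:1 (Protocol 9.2) and about 444 completing the double-blind period (Protocol synopsis).
- Placebo: 555/3 = 185. Reldesemtiv: 555 − 185 = 370.
- Share reaching the switch: 444/555 = 0.80, assumed equal in both arms. This gives 185 × 0.80 = 148 and 370 × 0.80 = 296.
- Let rP and rR be the proportions of those patients, in the placebo and reldesemtiv arms, with an AE that is ongoing at the switch and later moves into a given higher grade category. The amount carried back is 148·rP/185 = 0.80·rP for placebo and 296·rR/370 = 0.80·rR for reldesemtiv.
- Distortion of the difference (reldesemtiv minus placebo) = 0.80·(rR − rP).
- With rP = rR = 5%: placebo 7.4/185 = 4.0 points, reldesemtiv 14.8/370 = 4.0 points, distortion 0.

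**4. Scale in the placebo column (assumed rates, not in the documents).** Suppose 10% to 50% of the 148 have an AE ongoing at the switch, and 5% to 20% of those later worsen into a higher category.
- Low: 148 × 0.10 × 0.05 = 0.7 patients; 0.7/185 = 0.4 points.
- Middle: 148 × 0.30 × 0.10 = 4.4 patients; 4.4/185 = 2.4 points.
- High: 148 × 0.50 × 0.20 = 14.8 patients; 14.8/185 = 8.0 points.

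These are one-arm carry-back figures, not estimates of between-arm bias. They are upper values for their inputs, since a patient who already had another AE of that grade in the double-blind period adds nothing to a patient count.

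**The case against.** The strongest reply is that the rule is the same in both arms. An early-start AE that is Grade 1 before Week 24 and Grade 3 after it also carries Grade 3 back into the double-blind period. A reader might infer that the rule always makes reldesemtiv look safer. The documents do not support this: the effect on the comparison depends on rR − rP, and nothing in them gives its sign or size. What remains is a difference in kind. In the early-start arm both grades arose on reldesemtiv, so only timing is wrong; in the placebo column the treatment is wrong as well.

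A reader might also infer that the information is lost for good. That goes too far. AEs are reviewed at nearly every visit, serious worsening must be reported within 24 hours (8.3.1.7), interruptions and dose reductions are dated, and sites can be queried. The AE page itself does not hold the information, but much of it could be recovered with effort.

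Three further points limit the consequence, and they stand:
- The safety endpoint is incidence of AEs and serious AEs, and an AE that starts on placebo is properly a placebo-period AE. Safety analysis is descriptive.
- Laboratory values, including the renal and hepatic ones, are also summarized directly from the measurements (SAP 9.5).
- Expected signs of ALS progression are mostly not recorded as AEs (8.3.1.6, Table 4), which shrinks the pool.

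Finally, CRF completion instructions not included here might require a new record after the switch. If so, they would need reconciling with 8.3.1.3, which points the other way.

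**Conclusion.** The point holds as a defect in severity attribution. The protocol's capture rule merges grades from two treatments, and under either of the two assignment methods that the recorded data allow, the double-blind placebo column can show a grade reached on reldesemtiv. That the grade lands there rests on assignment by onset or by overlap; the documents state neither. That the worsening also vanishes from the active drug period follows only under assignment by onset.

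The exposure is mainly the by-severity tables, plus relationship and seriousness if these are updated on the same record. AE incidence, laboratory summaries and the efficacy analyses are not affected. No size can be taken from the documents: the 0.4 to 8.0 points for the placebo column rest wholly on the assumed rates, and the net between-arm effect is undetermined. It is worth correcting because severe-event counts may be small and the correction is simple.

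**What to change.** **Protocol 8.3.1.3 and the AE page instructions.** Add, for all patients in both arms: *An AE ongoing at the first dose of the active drug period that later increases in grade or becomes serious is entered as a new AE with onset on the date of the change. The original entry keeps the highest grade reached before that dose.* A dated grade change on the same record would serve equally well. All patients enter the active drug period at a known point, so applying the rule to everyone reveals no treatment assignment.

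**SAP 9.2.1.** Define a TEAE, state how an AE is assigned to a period, take the maximum grade within each period, and count post-switch worsening as treatment-emergent in the active drug period.

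**Cost.** Some extra AE records, a few sentences in each document, and retrospective queries for AEs that already span Week 24.
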